Protocol

Randomized Clinical Trial of Intraoperative ECMO versus Cardiopulmonary Bypass in Lung Transplantation

Amendment 1. September 27, 2017

TABLE OF CONTENTS

DEFINITIONS, ACRONYMS, AND ABBREVIATIONS.

ABSTRACT.

BACKGROUND AND SIGNIFICANCE

ENDPOINTS.

STUDY DESIGN.

STUDY POPULATION.

DEFINITIONS AND MEASUREMENT OF ENDPOINTS.

CLINICAL CENTERS.

DATA COLLECTION.

DATA MANAGEMENT

ANALYTIC PLAN.

REFERENCES.

DEFINITIONS, ACRONYMS, AND ABBREVIATIONS

CPB Cardiopulmonary bypass

ECMO Extracorporeal membrane oxygenation

PGD Primary Graft Dysfunction

STUDY INVESTIGATOR

PI: [name]

Co-Authors

[name]

[name]

[name]

[name]

[name]

[name]

[name]

[name]

ABSTRACT

Title	Randomized Clinical Trial of Intraoperative ECMO vs. Cardiopulmonary Bypass in Lung Transplantation
Background	Cardiopulmonary bypass (CPB) is the current standard of care for intraoperative cardiorespiratory support during lung transplantation. However, the blood-air interface and the need for full systemic anticoagulation may lead to systemic inflammatory response and coagulopathy. Some reports have suggested that intraoperative support with extracorporeal membrane oxygenation (ECMO) in lieu of CPB may be a better alternative with decreased bleeding, blood requirements and rates of primary graft dysfunction (PGD).
Hypothesis	patients on ECMO will have 
• decreased transfusion requirements,• decreased intubation time,• lesser PGD grade at 72 hours• No increase in major adverse events• Pump duration may be longer.
Study Design	A prospective randomized trial comparing intraoperative support with ECMO and CPB. This will be a superiority trial for efficacy and non-inferiority for safety. The allocation ratio will be 1:1.
Number of Participants	40 in each arm
Study Objectives	Determine if ECMO compared to CPB during lung transplantation has a beneficial effect on

	short term outcomes after lung transplantation.
Interventions	When patient need intraoperative cardiopulmonary support, patient would be randomized to ECMO or CPB
Inclusion Criteria	All patients undergoing lung transplantation. Not all patients randomized will need intraoperative support

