Currently, many centers would use one technique or the other and both are considered current standard of care and best practice. At Cleveland Clinic, we have used both methods. The method of support is currently not discussed with patients as both are considered acceptable.

HYPOTHESIS

Our hypothesis is that patients on ECMO will have a decreased transfusion requirements, decreased intubation time, lesser PGD grade at 72 hours without increase in adverse risk. Pump duration may be longer.

ENDPOINTS

Primary

- 1 Bleeding: total PRBC transfusion requirements at 72hours

Secondary

Superiority

1. Ventilation time (days)
2. Intraoperative PRBC transfusion rates
3. Duration of support
4. Primary graft dysfunction (PGD) grade at 72 hours.
5. Transfusion requirement of FFP, platelets, cryoprecipitate at 72 hours.

Non-inferiority:

1. Composite outcome of: 30-day or discharge date (if earlier than 30 days) mortality, bleeding requiring reoperation, new ECMO, new renal failure requiring dialysis

STUDY DESIGN

Randomized clinical trial with an allocation ratio of 1:1, comparing CBP versus ECMO for intraoperative cardiopulmonary support. Study will have a superiority design for efficacy and a non-inferiority design for safety.

Randomization:

All lung transplant patients will be consented preoperatively. Patients will be randomized at the beginning of the case and the configuration of the cardiopulmonary bypass machine will be set accordingly. Not all patients randomized will require intraoperative cardiopulmonary support.

Circuit design:

separate tubing that connects the venous return line directly to the pump head bypassing the venous reservoir. The venous reservoir is still connected and but clamped.

Incision and cannulation:

The type of incision will be at the discretion of the surgeon but can be sternotomy, thoracotomy or clamshell. If patient has a sternotomy and randomized to ECMO, venous cannula should be placed through a percutaneous femoral venous cannula to avoid the potential of air embolus.

Anticoagulation:

ACT target 200-250. Repeat every 30 min. Bolus 5000U, give supplemental doses as needed.

Conversion to full cardiopulmonary bypass:

Give full dose heparin; release the clamp on the venous reservoir after act is above 480.

Reasons to convert from ECMO to CPB intraoperatively:

- Significant bleeding to allow blood to return back to circuit

- Heart remain too distended to allow mobilization

- Air in the circuit

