- The need to fibrillate or arrest the heart

- Hemodynamic instability from positioning

Other safety mechanisms:

- Consider system for rapid transfusion

- Double lumen intubation: the heart does not decompress and there's ejection requiring the need for ventilation.

- Use an urchin or heartnet for heart positioning if necessary

- Once the patient is decannulated, the blood from the circuit can be re-transfused back into the patient

Transfusion triggers:

Transfusion triggers will be hematocrit of .24 and at the discretion of the staff surgeon, anesthesiologist or intensivist. Coagulopathy will be corrected based on Cleveland clinic post cardiectomy bypass protocol (appendix 2) and at the discretion of surgeon, anesthesiologist or intensivist.

Patients will be extubated at the discretion of the staff surgeon and intensivist.

Patients who are consented but not included in the study and patients who are felt to be better candidates for cpb will be followed in a separate registry

NUMBER OF PARTICIPANTS

40 Patients in each arm

Power calculation (based on 2015 CCF outcomes)

- Safety

 - 30 day mortality: 6.2%

Bleeding requiring reoperation: 10.3%
New ECMO: 1.3%
New renal failure requiring dialysis: 10.3%
Composite outcome 18.6%.

Sample size calculation
Non-inferior margin: 5%
90%: 283, 80%:205, 70%: 155
Non-inferior margin: 10%
90%: 77, 80%:56, 70%: 42

Efficacy

PGD grade at 72 h:

0:	24.4%
1:	47.4%
2:	14.1%
3:	14.1%

RBC transfusion

CPB: 14.7(8.4) vs ECMO 9.3(6.9)
90%: 51, 80%:39, 70%: 30

Ventilation time

CPB: 16.5days (27.3) vs ECMO 8.25 (16.4)
90%: 83, 80%:62, 70%: 49

For literature outcomes, see appendix 1.

STUDY POPULATION

The study population will be all patients undergoing lung transplantation at our institution. These patients will be randomized using the block method and allocated to either the CPB or ECMO group. Not all patients randomized will require intraoperative support.

Inclusion Criteria

All consented patients undergoing lung transplantation.

Exclusion Criteria

Patients undergoing concomitant cardiac operations with indication for obligate use of cardiopulmonary bypass

Patient with specific anatomy that require full cardiac decompression such as severe pulmonary hypertension or large heart that are shifted severely into the left chest (relative)

Patients with high likelihood of significant pleural bleeding that will require returning the blood back into the cardiotomy reservoir (relative)

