Patients bridged to transplant with ECMO

Cystic fibrosis/bronchiectasis/resistant infection patients where surgeon will need to remove both lungs prior to implantation

Patients who the surgeon feels would be better served with CPB rather than ECMO
These patients will be entered into a registry and followed.

CLINICAL CENTERS

Patient Confidentiality

All patient records will be kept confidential according to HIPAA guidelines. Study investigators and site Institutional Review Boards (IRBs) may review source documentation as necessary, but will then transmit this information to Clinical Investigations at Cleveland Clinic according to the patient's unique study number. Linkage of that study number to the actual patient will reside only at the individual institutions. Aggregate data from this study may be published as per publication policy documented in the trial agreements; no data with patient identifiers will be published.

Consent

Patients will be consented for surgery ahead of time at time of listing

DATA COLLECTION

Data will be collected from Epic Systems chart review and supplemental data collection. All necessary data are currently already collected. Study terminates at patient discharge. No additional testing or followup is needed beyond what is already done for this patient population.

DATA MANAGEMENT

The data will be stored in Red Cap Sheets strictly secured and managed by the lead and other co-investigators. No identifiable information will be shared with outside parties, ensuring that all data will remain safely stored on Cleveland Clinic Main Campus user hard drives and will only be shared amongst our study team.

ANALYTIC PLAN

Basic statistical analysis will be required to compare the outcomes in the groups. Patients who are excluded will be included in a separate registry.

Analysis will be based on intention to treat.

A statistical significant difference is defined as a two-sided P value less than 0.05.

REFERENCES

1. Machuca (2015) Outcomes of intraoperative extracorporeal membrane oxygenation versus cardiopulmonary bypass for lung transplantation.
2. Bermudez (2014) Outcomes of Intraoperative Venoarterial Extracorporeal Membrane Oxygenation Versus Cardiopulmonary Bypass During Lung Transplantation.
3. Ius (2012) Lung transplantation on cardiopulmonary support: Venoarterial extracorporeal membrane oxygenation outperformed cardiopulmonary bypass.

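### The safety sample sizes do not follow from the stated 18.6% composite rate (3.4- to 4.8-fold too small if true rates are equal), and the plan gives no rule for concluding non-inferiority

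*Combined protocol and SAP*

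**What the plan says.** The Abstract (Study Design) states: "This will be a superiority trial for efficacy and non-inferiority for safety". The Study Design section repeats it: "Study will have a superiority design for efficacy and a non-inferiority design for safety". The Abstract's hypothesis includes "No increase in major adverse events". The only endpoint listed under non-inferiority is the secondary composite of mortality (to 30 days, or to discharge if earlier), reoperation for bleeding, new ECMO and new dialysis.

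Under Number of Participants, the safety part of the power calculation uses the centre's 2015 outcomes. It gives the four component rates and then "Composite outcome 18.6" per cent. Sample sizes for three levels of power follow:

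- 5% margin: "90%: 283, 80%:205, 70%: 155"
- 10% margin: "90%: 77, 80%:56, 70%: 42"

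The section does not give the alpha, the test, the expected ECMO rate or the scale of the margin. It does not say whether n is per arm, or which margin applies. Enrolment is 40 per arm.

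The Analytic Plan specifies basic statistical analysis, intention to treat, and one criterion: "A statistical significant difference is defined as a two-sided P value less than 0.05".

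**The concern.** An event rate of 18.6% has a large binomial variance, and sizes such as 77 or 42 per arm look far too small for a 10-point margin. If they are wrong, the table misstates what the trial can show about safety. A reader who sees 42 per arm beside 70% power would take 40 per arm as close to 70%.

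The missing decision rule makes this worse. With no chosen margin and no confidence-limit criterion, the margin could be picked after the data are seen, or an absence of harm could be inferred from a non-significant difference test. The composite covers death, reoperation, new ECMO and dialysis, so an unsupported reassurance would matter.

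**Working it through.** **Inputs.** From Number of Participants: composite 18.6%; margins 0.05 and 0.10; 40 per arm; allocation 1:1. Assumed, because the plan is silent: absolute margins, n per arm, 18.6% as the CPB rate, and first an equal ECMO rate. Both common alphas are shown, since none is stated for non-inferiority.

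**Is n per arm?** The neighbouring RBC line reads "90%: 51, 80%:39, 70%: 30". With SD 8.4 in both arms, difference 14.7 − 9.3 = 5.4 and two-sided 0.05, n = 2·8.4²·(1.960+z_β)²/5.4² = 50.9/38.0/29.9. The line is reproduced per arm to within one patient. If the safety figures were totals, the shortfall would double.

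**Required n with equal rates.** The formula is n = (z_α+z_β)²·[p_C(1−p_C)+p_E(1−p_E)] / (margin − (p_E−p_C))².

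With p_C = p_E = 0.186 the variance term is 2·0.186·0.814 = 0.3028. For one-sided 5%, 90% power and a 10-point margin: (1.645+1.282)²·0.3028/0.01 = 259.3, so 260.

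| Margin | Power | Printed | One-sided 5% (ratio) | One-sided 2.5% (ratio) |
|---|---|---|---|---|
| 5 points | 90% | 283 | 1038 (3.7) | 1273 (4.5) |
| 5 points | 80% | 205 | 749 (3.7) | 951 (4.6) |
| 5 points | 70% | 155 | 570 (3.7) | 748 (4.8) |
| 10 points | 90% | 77 | 260 (3.4) | 319 (4.1) |
| 10 points | 80% | 56 | 188 (3.4) | 238 (4.2) |
| 10 points | 70% | 42 | 143 (3.4) | 187 (4.5) |

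A more lenient alpha does not rescue the table: one-sided 10% still needs 796/546/395 and 199/137/99.

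**Could an assumed ECMO benefit explain the table?** Let d = p_C − p_E. For any fixed alpha, power and pair of rates, the ratio between the two rows is ((0.10+d)/(0.05+d))². The printed ratios are 283/77 = 3.68, 205/56 = 3.66 and 155/42 = 3.69, which give d of about 0.4 to 0.5 points, that is, nearly equal rates. At d = 0.0045 (ECMO 18.15%), one-sided 5% and 90% power need about 865 and 236 per arm, still about three times the printed figures. Fitting each row separately at one-sided 5%:

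- ECMO 14.5% gives 285/206/157 at 5 points (fits) but 119/86/66 at 10 points (does not).
- ECMO 11.8% gives 78/56/43 at 10 points (fits) but 158/114/87 at 5 points (does not).

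**Could a component rate have been used?** At one-sided 5% and 10 points, 6.2% in both arms gives 100/72/55, 10.3% gives 159/115/87 and 1.3% gives 22/16/13. None fits. Equal rates of about 4.3% (5-point row) and 4.7% (10-point row) would come close, but the safety list contains no such rate.

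**Actual power.** Power = Φ((margin − (p_E−p_C))/SE − z_α). At equal rates of 18.6%:

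| n per arm | Margin | Labelled power | One-sided 5% | One-sided 2.5% |
|---|---|---|---|---|
| 283/205/155 | 5 points | 90/80/70% | 45/37/30% | 33/26/20% |
| 77/56/42 | 10 points | 90/80/70% | 48/39/32% | 36/27/22% |
| 40 | 5 points | – | 14% | 8% |
| 40 | 10 points | – | 31% | 21% |

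At 40 per arm, SE = √(0.3028/40) = 0.0870, so the 95% CI half-width is 1.96·0.0870 = 17 points, wider than either margin.

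**What the stated criterion would do.** If the true rates were 18.6% and 28.6%, the two-sided 0.05 test (pooled z, exact enumeration) at 40 per arm has power 0.183. It would be non-significant about 82% of the time despite a true 10-point increase.

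**The case against.** Several points can be made for the plan.

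- **Alpha.** The upper part of the 3.4- to 4.8-fold range depends on one-sided 2.5%, which the plan does not state for non-inferiority. The table's spacing favours one-sided 5%: the 90%-to-70% ratio is 1.83 in both rows, against 1.82 expected at one-sided 5% and 1.70 at 2.5%. This is fair. If one-sided 5% was intended, the shortfall is 3.4- to 3.7-fold.
- **Equal rates.** The 18.6% is a centre-wide 2015 figure, the centre has used both methods, and no ECMO rate is given. The fold-error and power figures are therefore conditional. With CPB at 18.6% and a 10-point margin, power at 40 per arm (one-sided 5% / 2.5%) rises to 52% / 40% if ECMO is truly 14.5%, 68% / 56% at 11.8% and 77% / 67% at 10%. That stands, but no single such benefit reproduces both printed rows.
- **Importance.** The composite is secondary, all six printed safety figures exceed 40, and 40 per arm tracks the RBC figure of 39 at 80% power. Nothing says that 40 was chosen for safety. This limits the damage to the safety claim.
- **Two issues.** The absent decision rule is an analysis omission, separate from the arithmetic, and it is the part that could directly distort a conclusion. That is right, and it would need fixing even if the table were correct.

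**Conclusion.** The concern holds. The printed safety sample sizes cannot be derived from 18.6%, either with equal rates or with any one ECMO rate paired with it. With equal true rates, absolute margins and n per arm, they are too small by 3.4- to 3.7-fold at one-sided 5% and by 4.1- to 4.8-fold at one-sided 2.5%. Power at the printed sizes is 20% to 48%, against the labelled 70% to 90%.

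Separately, two margins are listed and neither is chosen, and the only stated criterion tests for a difference, so the plan has no means of concluding non-inferiority. This must be fixed, because non-inferiority for safety is a declared design feature. Sizing for the primary endpoint is not affected.

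**What to change.** 1. Replace the safety lines with figures that carry their assumptions, for example: *Composite (secondary), 18.6% in both arms, one-sided alpha 2.5%, per arm for 90/80/70% power: 5-point margin 1273/951/748; 10-point margin 319/238/187. At 40 per arm, power is 8% (5 points) or 21% (10 points).* If one-sided 5% is intended, use 1038/749/570 and 260/188/143, with power 14% and 31%. If a lower ECMO rate is assumed, state it and its source.
2. The investigators should name one margin, state its scale and justify it.
3. Add to the Analytic Plan: *Non-inferiority on the composite is claimed only if the upper limit of the 95% CI for the risk difference (ECMO minus CPB) is below the named margin. Otherwise the difference and its CI are reported as an estimate, with no claim of non-inferiority or of no increase.* The 95% interval matches one-sided 2.5%; one-sided 5% would need a 90% interval.
4. If safety is reduced to estimation, amend the non-inferiority wording in the Abstract, Endpoints and Study Design to match.

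The cost is wording and corrected figures, with no extra patients. The stated safety power becomes much less favourable, and the non-inferiority claim may have to give way to estimation.

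### Each efficacy sample size silently uses only one of its two printed SDs: conservative for RBC transfusion, but for ventilation time the sizes are little more than half of what the printed SDs require

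*Combined protocol and SAP*

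**What the plan says.** The section NUMBER OF PARTICIPANTS plans "40 Patients in each arm" and attributes its inputs to the institution's own data: "Power calculation (based on 2015 CCF outcomes". Two efficacy calculations follow.

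- **RBC transfusion.** The inputs are "CPB: 14.7(8.4) vs ECMO 9.3(6.9" (closing bracket omitted here), and the sizes for three power levels are "90%: 51, 80%:39, 70%: 30". The ENDPOINTS section makes this the primary endpoint: "Bleeding: total PRBC transfusion requirements at 72hours".
- **Ventilation time.** The inputs are 16.5 days (27.3) for CPB and 8.25 (16.4) for ECMO, and the sizes are "90%: 83, 80%:62, 70%: 49". ENDPOINTS lists this first among the secondary superiority endpoints.

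STUDY DESIGN gives the allocation: "Randomized clinical trial with an allocation ratio of 1:1". ANALYTIC PLAN gives the significance level: "A statistical significant difference is defined as a two-sided P value less than 0.05". The protocol names no formula or test for either calculation, does not say which SD was used, and does not state the power expected at 40 per arm.

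**The concern.** When a plan prints one SD per arm, the reader expects both to enter the calculation. Here neither set of sizes follows from both. The primary-endpoint line appears to ignore the ECMO SD, and the ventilation line appears to ignore the CPB SD. A single rule, such as always using the control-arm SD or always using the larger SD, would explain the first line but not the second.

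The direction decides what is at stake. Using the larger SD overstates the need and leaves a margin. Using the smaller SD understates the need and credits the trial with power it does not have. A reader who takes the ventilation line at face value would place 40 per arm somewhat below the 49 listed for 70% power, and would read a null result on ventilation time as more informative than it would be.

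**Working it through.** **Inputs.** Two-sided 0.05 (ANALYTIC PLAN); 1:1 allocation (STUDY DESIGN); means and bracketed values from the power calculation, with the brackets read as SDs; printed sizes read as per arm.

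**Formula.** n per arm = (z₀.₉₇₅ + z_power)² × (s₁² + s₂²) / d². The first factor is 10.507, 7.849 and 6.172 for 90%, 80% and 70% power.

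**RBC transfusion.** d = 14.7 − 9.3 = 5.4 and d² = 29.16.

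| SDs used | s₁² + s₂² | 90% | 80% | 70% |
|---|---|---|---|---|
| Printed in plan | – | 51 | 39 | 30 |
| 8.4 in both arms, normal | 141.12 | 50.9 | 38.0 | 29.9 |
| 8.4 in both arms, t | 141.12 | 51.8 | 39.0 | 30.9 |
| 8.4 and 6.9, normal | 118.17 | 42.6 | 31.8 | 25.0 |

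A common SD of 8.4 reproduces the plan's figures to within one patient. Rounded up, both SDs give 43/32/26, or 44/33/27 by Welch t. A common SD of 6.9 gives only 35/26/21.

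Power at 40 per arm for 5.4 units is 81.0% (t) with 8.4 in both arms and 87.3% (Welch t) with 8.4 and 6.9. The normal approximation gives 82.0% and 88.1%.

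**Ventilation time.** d = 16.5 − 8.25 = 8.25 and d² = 68.06.

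| SDs used | s₁² + s₂² | 90% | 80% | 70% |
|---|---|---|---|---|
| Printed in plan | – | 83 | 62 | 49 |
| 16.4 in both arms, normal | 537.92 | 83.0 | 62.0 | 48.8 |
| 27.3 and 16.4, normal | 1014.25 | 156.6 | 117.0 | 92.0 |
| 27.3 in both arms, normal | 1490.58 | 230.1 | 171.9 | 135.2 |

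Of these, only the smaller SD in both arms reproduces the plan's figures, and it does so after ordinary rounding. Rounded up, both SDs give 157/117/92, or 158/119/94 by Welch t.

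Power with SDs 27.3 and 16.4, by Welch t:

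| n per arm | Power claimed | Power from both SDs |
|---|---|---|
| 83 | 90% | 65% |
| 62 | 80% | 52% |
| 49 | 70% | 43% |
| 40 (planned) | not stated | 36% |

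Hand check at 40 per arm: the standard error is √(1014.25/40) = 5.04, so 8.25/5.04 = 1.64. Since 1.64 − 1.96 = −0.32, power is about 37% by the normal approximation, in line with the 36% from Welch t. With 16.4 in both arms, as the plan's sizes imply, the standard error is √(537.92/40) = 3.67 and power would be about 61%.

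**The case against.** The strongest objection is that the RBC line is not wrong. Taking the larger, control-arm SD as common to both arms is a recognised and cautious choice, and it reproduces 51/39/30 to within a patient. This stands. A reader might infer from the unused SD of 6.9 that the primary-endpoint size is an arithmetic error, or that 40 per arm is unsound. The documents support neither inference. The plan commits to no formula, states no power at 40 per arm that could be misstated, and has at least the power suggested by its 80% row under either SD choice.

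A second objection is that back-calculation cannot prove the method. For RBC this is fair. The two-SD sizes multiplied by 1.2 would give 51.1/38.2/30.0, as close a match as the common SD, although the protocol mentions no such inflation. For ventilation no similar escape exists: the printed sizes lie far below the two-SD requirement, so any added allowance would widen the gap.

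A third objection is that ventilation time is secondary and 40 per arm was not chosen to satisfy it, since 40 falls short even of the printed 49. This is true and limits the consequence. It does not make the printed sizes correct, because the protocol still attaches 90%, 80% and 70% to sizes that its own inputs do not support.

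Finally, stating 87% for RBC could look optimistic, because not every randomised patient will need support, conversion from ECMO to CPB is allowed, and analysis is by intention to treat. That is a reason to label the figure as before dilution, not a reason to leave the SD assumption unstated.

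**Conclusion.** The point holds as an undeclared and inconsistent use of the printed SDs, with a material error on the ventilation line only.

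- **RBC (primary).** The sizes are conservative and defensible. What is missing is the assumption behind them. Power at 40 per arm is about 81% or about 87%, depending on that assumption.
- **Ventilation time (secondary).** The sizes are wrong as written: 83/62/49 against about 157/117/92, so the claimed 90/80/70% is about 65/52/43%. The planned 40 per arm has about 36%.

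A reader might go further and conclude that the trial is underpowered or should enrol more patients. On the printed inputs that does not follow: the primary endpoint is adequately served, and the protocol nowhere says that 40 per arm was meant to power ventilation time.

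The figures assume that the bracketed values are SDs, that the sizes are per arm, that means are compared at two-sided 0.05, and that the full treatment difference is seen. Unsupported or converted patients may dilute that difference; no allowance for this is included.

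**What to change.** Apply one formula with an SD for each arm, at two-sided 0.05, to both endpoints, and name the test.

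1. **Ventilation time:** replace 83/62/49 with 157/117/92 (158/119/94 by Welch t), and state that 40 per arm gives about 36% power for 8.25 days.
2. **RBC transfusion:** choose one of two acceptable options. Either print 43/32/26 (44/33/27 by t) with about 87% power at 40 per arm, or keep 51/39/30, state that a common SD of 8.4 was assumed as a deliberate exception to the per-arm formula, and give about 81%.
3. State that these powers are before any dilution from patients who receive no support or are converted.

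The cost is a line or two of protocol text. Enrolment does not change. The one drawback is a less favourable stated power for a secondary endpoint.

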a. Excluded: patients bridged w extracorporeal life support, required emergency cannulation for cardiopulmonary support, concomitant cardiac procedure/transplant, B cenocepacia; b. Matched: age, lung transplantation indication, procedure type (bil/single), Recipient factors similar (BMI, gender, donor info) c. Outcomes i. Perioperative: blood product transfusion ii. Early outcomes: mechanical ventilation requirement, ICU stay, hospital stay iii. 90day mortality (33 ECMO matched with 66 CPB)

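### Planned procedure (single or bilateral) is neither a stratification factor nor a covariate, which gives up a modest amount of precision in the 72-hour PRBC comparison

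*Combined protocol and SAP*

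**What the plan says.** The inclusion criterion under Study Population is "All consented patients undergoing lung transplantation". The exclusions do not remove single-lung procedures, so both types enter. Study Design describes a "Randomized clinical trial with an allocation ratio of 1:1", and Number of Participants sets "40 Patients in each arm". The allocation method is given in one sentence: "These patients will be randomized using the block method and allocated to either the CPB or ECMO group". Nothing is said about strata or block size.

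The primary endpoint is "Bleeding: total PRBC transfusion requirements at 72hours". The Analytic Plan promises basic statistical analysis by intention to treat with a two-sided 5% threshold. It names no test, model or covariate.

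Appendix 1 bears on procedure type in two places. The summary of the 33 v 66 comparison reads "Matched: age, lung transplantation indication, procedure type (bil/single", and two of the literature tables give ischemic times separately for single-lung cases. No table gives transfusion, or need for support, by procedure.

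**The concern.** Blocking equalises the arm totals. Unless the blocks are stratified, the mix of single and bilateral cases in each arm is left to chance. If bilateral cases use more red cells, an arm that happens to hold more of them will show more transfusion whatever the circuit. With 80 patients, visible imbalances are common, and the plan has no covariate to absorb them. A source of variation that should be known before the case starts would then stay in the error term of the primary comparison. At stake is some of the power of a trial whose sample size, on the plan's own figures, sits just above the 80% requirement.

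**Working it through.** **Inputs from the documents.** Number of Participants gives "CPB: 14.7(8.4) vs ECMO 9.3(6.9" (read as mean and SD, in units) and, for 90, 80 and 70% power, "90%: 51, 80%:39, 70%: 30" per arm. The difference is 14.7 − 9.3 = 5.4 units. Alpha is 0.05 two-sided (Analytic Plan).

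**Assumed inputs, not in the documents.** Bilateral share p = 0.5 to 0.8. Bilateral-minus-single difference D = 3 to 8 units, the same in both arms.

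**1. Reproduce the plan's figure.** n per arm = 2 × 8.4² × (1.96 + z)² / 5.4². This gives 50.9, 38.0 and 29.9, so 51, 38 and 30. The noncentral t version gives 52, 39 and 31. The printed 51, 39 and 30 agree to within one patient. The pooled SD, √((8.4² + 6.9²)/2) = 7.69, gives 43, 32 and 26 and does not fit. The plan therefore used 8.4 for both arms.

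**2. Power at 40 per arm without adjustment.**
- SD 8.4 in both arms: SE = 8.4 × √(2/40) = 1.88; t-test power 81.0% (82.0% by the normal approximation).
- Printed SDs: SE = √((8.4² + 6.9²)/40) = 1.72; Welch power 87.3%.

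**3. Chance imbalance in procedure mix.** Splitting 80 patients, 80p of them bilateral, into 40 and 40 at random is a hypergeometric draw. Small blocks that ignore procedure give nearly the same result.

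| Bilateral share | More than 10 points | 10 points or more | 20 points or more |
|---|---|---|---|
| 50% | 26% | 50% | 12% |
| 70% | 22% | 46% | 9% |
| 80% | 16% | 40% | 5% |

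A 10-point imbalance shifts the arm difference by 0.1 × D: 0.4 units if D = 4 and 0.8 if D = 8, against an SE of 1.88 and a planned effect of 5.4.

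**4. Power with adjustment.** Residual variance = SD² − p(1−p)D². For p = 0.7 and D = 5, 0.21 × 25 = 5.25; 70.56 − 5.25 = 65.31; residual SD 8.08.

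| p | D | Variance removed | Power, SD 8.4 in both arms | Power, SDs 8.4 and 6.9 |
|---|---|---|---|---|
| no adjustment | – | 0 | 81.0% | 87.3% |
| 0.8 | 3 | 1.44 | 81.8% | 88.1% |
| 0.7 | 3 | 1.89 | 82.1% | 88.3% |
| 0.7 | 5 | 5.25 | 83.9% | 90.1% |
| 0.7 | 8 | 13.44 | 88.4% | 94.1% |
| 0.5 | 8 | 16.00 | 89.8% | 95.3% |

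Outside the assumed range, with 90% bilateral and D of 2 to 6, the gain is 0.2 to 1.8 points.

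**5. Stratifying or adjusting?** Simulation with 8,000 trials per cell, 80 patients, blocks of 4, SD 8.4 and p = 0.7:

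| | D = 4 | D = 8 |
|---|---|---|
| Neither | 81.0% | 81.0% |
| Stratified blocks only | 81.7% | 84.3% |
| Adjustment only | 82.6% | 87.3% |
| Both | 83.0% | 88.9% |

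The simulation error of each power figure is about √(0.81 × 0.19/8000) = 0.4 points, so the smallest gaps at D = 4 should not be over-read. Type I error with neither measure was 0.049 to 0.051. With stratified blocks and an unadjusted test it fell to 0.044 (D = 4) and 0.031 (D = 8).

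**The case against.** The strongest objection is that the premise is not in the documents. A reader might infer that procedure type is a known driver of transfusion and of the need for support. The documents show neither. Matching in a retrospective comparison guards against confounding by the choice of circuit, and that study matched on age and indication as well, so it does not single out procedure type. This stands, and it is why p and D are labelled as assumptions.

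Second, a reader might infer that the comparison is biased or the sample size wrong. Neither follows. Type I error stays near 5%, chance imbalance is already in the standard error, and the red-cell sample size reproduces. The power figures are said to rest on the centre's 2015 outcomes. If 8.4 came from a mixed single and bilateral series, which is not stated, 40 per arm already pays for this noise and adjustment adds reserve. This stands too.

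Third, a reader might argue that an arm with more bilateral cases would also hold more supported patients. That depends on when patients are randomised. The Interventions row of the Abstract places it at the moment support is needed, so every randomised patient would need support. The Randomization paragraph of Study Design places it at the start of the case and adds that some patients will not need support. The two must be reconciled. The precision argument applies under either.

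Finally, the protocol's silence on strata does not prove that none will be used. The point is that none is named, in the allocation or in the analysis.

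**Conclusion.** The point holds as a low-cost gain in precision. Under the assumed 50-80% bilateral share and 3-8 unit difference, adjustment lifts power at 40 per arm from 81% to about 82-90% on the SD the plan used, or from 87% to 88-95% on the two printed SDs. At about 70% bilateral and 3-5 units, the gain is about 1-3 points. At that share it reaches about 7 points only when the difference is near 8 units. Most of it comes from the analysis; stratified blocks alone recover less.

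The calculation treats the printed SDs as totals that include the variation between procedures. If they came from one procedure only, the unadjusted comparison would fall below 81%, and adjustment would bring it back to about that level. The centre's own records can settle p, D and the make-up of the planning series.

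**What to change.** In the Analytic Plan, add: *The arm comparison of PRBC units transfused to 72 hours will be adjusted for planned procedure (single or bilateral), as recorded before randomisation.* The planned procedure should be used rather than the one performed, so that the covariate cannot be affected by allocation. It should be available from the chart review already planned. If enrolment has begun, this can still be adopted for all patients, provided it is fixed before outcomes are examined by arm.

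In Study Population, amend the allocation sentence to: *Patients will be randomised 1:1 in permuted blocks stratified by planned procedure (single or bilateral).* If the trial is under way, apply this from the amendment onward. Do not stratify without the adjustment, because the unadjusted test then becomes conservative.

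The cost is a second randomisation list and one model term; 80 patients can carry two strata. Since no primary model is named at present, one has to be specified before a term can be added to it.

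Separately, reconcile the Abstract and Study Design on the time of randomisation before making any argument about need for support.
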